Prior to EPN Hour 0, set up SUPPER Tablet at bedside. Open the SUPPER Titration and enter all of the patient demographics, formula, TPN, and fluid information at the top. Calculate Schofield 100% BMR (height/weight). Rates for EN, PN, Lipids, and remaining available hourly fluids will populate. Print SUPPER Titration for bedside and study binder and review with the bedside nurse. A new SUPPER Titration Tool will need to be created for any change in formula kcal content, calorie goal, or new total fluid order (such as in the case of fluid restriction). As EN feeds are advanced, PN and Lipids decrease. If EN is held or reduced, titrate PN and Lipids according to SUPPER Titration sheet. Choice of PN is based on patient age. If the patient is 1 year of age or older, patients will receive Baxter Clinimix. Patients between 1 month of age and <1 year of age will receive in-house custom PN. The early EN guideline in place for clinical use at CHOP will be used to increase enteral feeds. The goal should be to reach full enteral feeds within 48 hours of initiating EN.

The SUPPER Algorithm uses Schofield's equation to calculate the initial kcal/day goal. Patients are to initially receive a max of 75% of calorie goal and 1.5 gm/kg/day protein for the first 24 hours. Patients will receive 100-120% of MREE (or 100-120% of Schofield predicted BMR in the setting of no MREE) and 2-3gm/kg/day protein with combined PN and EN by study day 2, not to exceed 1600mL/M²/day in fluids (See Table at end of MOO). If there is >20% discrepancy between the unit dietician's usual practice for determination of kcals/day for a given patient and the Schofield predicted BMR, please call the U of A PI to discuss altering the individual patient's kcal goal during the 7-day study intervention. The bedside nurse will titrate PN to maintain calorie goal and protein every 4 hours with the aid of the SUPPER Titration Sheet in place of usual total IVF orders. As patient tolerates increased EN, PN and IL are decreased. In this manner, in the Early PN arm, the patient's delivered calories and protein remain constant, although the route of delivery changes as enteral feeds advance.

	0 Hour	12 Hour	24 Hour	48 Hour	72 Hour	96 Hour	120 Hour	144 Hour	168 Hour
Blood Sample 2mLs	X	X	X	X	X	X	X	X	X
Fecal Samples (if patient has stool)	X		X	X	X	X	X	X	X
Metabolic Cart (REE)	Occurs Between 0 hour and 48 hours (DCMC Only)					Occurs Between 96 hours and 144 hours (DCMC Only)			

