Aim 2. We will assess differences between FABP2, claudin 3, citrulline, lactulose/mannitol ratios, and by study arm. Descriptive plots: serum biomarker (y-variable) over time (x-variable) will be fit, with linear and smoothing splines. Plots are qualitative. Splines allow examination of possible nonlinear relationships and can be used to specify nonlinear or change-point models. We utilize one-way repeated measures ANOVA with the intestinal barrier assays as continuously measured outcomes and time (1,2,3,5, and 7 days) as explanatory variables. If the slope of the serum biomarkers is linear, then change in the slope over time will be calculated using a linear mixed effects model with an AR(1) variance-covariance structure. The variance-covariance structure allows for measurements taken closer together to be more similar than those farther apart in time, and adjusts the standard errors for this correlation. If the relationship between the serum biomarker is not linear in time, then change-point or nonlinear mixed effects models will be used. Aim Multivariable regression analysis will evaluate possible effect modification, or mediation, for non-invasive measures of intestinal epithelial barrier function. Effect modifiers are the interactions with PN group; mediators are those variables that could have a potential additive effect with the PN group. Additionally we will assess any potential confounding that might be present by assessing the change in the parameter estimate for the PN group effect. Potential modifiers, mediators, and confounders, include clinical variables, center effects, and severity of illness. We will test associations between measures of intestinal function and clinical variables, severity of illness, as well as dose and route of nutrition. With 40 subjects total, we will be able to include up to 4 possible predictors; therefore, if effect modifiers are warranted, model simplification will be necessary. If the study is stopped early the analysis plan may be modified due to small sample size.

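### The Aim 2 regression defines mediators and confounders in ways that cannot tell them apart, so a variable changed by arm could end up adjusted for in the PN-group estimate

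*Combined protocol and SAP*

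**What the plan says.** The multivariable regression in the Statistical Analysis Plan, Aim 2, gives variables three roles:

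- **Effect modifiers.** "Effect modifiers are the interactions with PN group". This is the usual definition.
- **Mediators.** "mediators are those variables that could have a potential additive effect with the PN group". Nothing is said about the variable being changed by arm or lying between arm and outcome.
- **Confounders.** "Additionally we will assess any potential confounding that might be present by assessing the change in the parameter estimate for the PN group effect". No size of change is given, and the plan does not say whether a flagged variable stays in the model.

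One list serves all three roles: "Potential modifiers, mediators, and confounders, include clinical variables, center effects, and severity of illness". It carries no restriction to values recorded before randomization. A separate sentence follows: "We will test associations between measures of intestinal function and clinical variables, severity of illness, as well as dose and route of nutrition". The model is limited to 4 predictors for 40 subjects.

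Aim 2 opens by promising a comparison of the barrier markers between arms. The repeated-measures ANOVA and the mixed models described next name time as the explanatory variable; none of them names arm.

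**The concern.** A mediator is a variable that arm changes and that in turn changes the outcome. An additive effect alongside arm is only what an independent predictor has, whether or not arm influences it. The mediator rule would therefore admit an ordinary baseline prognostic covariate.

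The confounder rule errs in the other direction. Among randomized patients, a pre-randomization variable can be out of balance only by chance. A variable that arm truly changes will shift the arm estimate systematically once it is entered, so it is the most likely kind of variable to be flagged.

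The list leaves room for such variables. The daily data collection forms record clinical data on each intervention day after randomization, and the plan does not say which time point of the clinical or severity variables is meant. If a variable of this kind is kept, the PN coefficient no longer estimates the total effect of early versus late PN. It estimates the part that does not pass through that variable.

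**Working it through.** **The plan's own figure.** The only number attached to this regression is the limit of 4 predictors. It is reproduced by 40 / 10 = 4 if ten subjects per predictor is assumed; the plan states no such ratio. The argument does not depend on it, but the fix must respect it.

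**Algebra.** Let T be arm (0/1), M a candidate variable and Y a barrier marker:

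- M = a·T + error
- Y = d·T + b·M + error

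Without M in the model, the arm coefficient estimates d + a·b, the total effect. With M in the model, it estimates d, the direct effect. The proportional change is −a·b / (d + a·b). If M is a baseline variable, a = 0 and the expected change is zero.

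**Inputs.** From the plan: 40 subjects. Assumed, because the documents give no effect size or SD for Aim 2: 20 per arm, residual SDs of 1, b = 0.8, total effect 1.0, two-sided alpha 0.05, and a rule that flags a change above 10% (20% also checked). Each patient contributes one outcome value, a simplification of the repeated samples. There were 5,000 simulated trials per row.

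The total is 1.0 in each scenario:

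- full mediation: 0 + 1.25 × 0.8 = 1.0
- half: 0.5 + 0.625 × 0.8 = 1.0
- quarter: 0.75 + 0.3125 × 0.8 = 1.0
- baseline covariate: 1.0 + 0 × 0.8 = 1.0

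| Role of M | Arm estimate without M | With M | Flagged at 10% | Flagged at 20% | Power without M | Power with M |
|---|---|---|---|---|---|---|
| Full mediator | 1.00 | 0.00 | 100% | 100% | 0.68 | 0.05 |
| Half mediator | 1.00 | 0.49 | 97% | 92% | 0.67 | 0.30 |
| Quarter mediator | 1.01 | 0.76 | 84% | 64% | 0.68 | 0.63 |
| Baseline prognostic, no mediation | 0.99 | 1.00 | 69% | 43% | 0.67 | 0.86 |

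**Reading the table.**

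1. The confounder rule flags mediators in most trials, and more often the more of the effect they carry.
2. It also flags a baseline covariate in 69% of trials, through chance imbalance. When the simulation was repeated with 20,000 patients, that flagging fell to 0%, while the full and half mediators were still flagged in 100%.
3. The additive-effect rule does not discriminate. M was a significant additive term in about 99% of trials in all four rows, including the one with no mediation.
4. Adjusting for a baseline prognostic covariate leaves the arm estimate at about 1.0 and raises power from 0.67 to 0.86. Baseline adjustment is therefore not the problem; the missing restriction to baseline values is.

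**The case against.** The case for leaving the text alone has five parts.

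- **Dose and route of nutrition.** A reader might infer that the plan would adjust the arm effect for these, the clearest consequences of arm: early-arm patients start PN within 2 hours of randomization, and late-arm patients receive it only from hour 96 if short of the calorie target. In the early arm the route also shifts by design ("although the route of delivery changes as enteral feeds advance"). But dose and route stand in the sentence on associations ("severity of illness, as well as dose and route of nutrition"), not in the confounder list. The documents do not support saying that they would enter as confounders. They are not excluded either.
- **Retention.** A reader might infer that flagged variables are kept. The plan says only that confounding will be assessed. The 10% and 20% rules above are assumptions, so the most that can be said is that a mediator would be flagged and could be kept.
- **Loss of the randomized effect.** A reader might infer that Aim 2's arm effect would be erased. The by-arm comparison at the start of Aim 2 is separate and would still address the total effect. This protection is thin, because no model with an arm term is specified for it; the regression is the only Aim 2 model said to contain a PN-group effect.
- **A legitimate use for confounding assessment.** Under Interim Safety Analysis, if Aim 1 is stopped, Aim 2 continues in patients whose EN and PN timing follows usual care. For them PN timing is not randomized and confounding is a real question. This point stands, and the fix allows for it.
- **Context.** This is a pilot, Aim 2b seeks effect modifiers, and those are defined correctly. Placing the regression under Aim 2b is itself an inference, since its sub-aim label is incomplete in the text. This lowers the stakes but does not repair the two definitions.

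**Conclusion.** The point holds as a fault in the stated rules. The mediator definition fits any independent predictor, the confounder criterion is met by mediators, and the shared list is not confined to pre-randomization values. A variable changed by arm would be flagged and could be kept, and a baseline covariate could be reported as a mediator.

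The size depends on how much of the effect passes through the variable. Under the assumed values, the regression's arm estimate falls from about 1.0 to 0.76, 0.49 or 0.00 for quarter, half or full mediation. The zero follows directly from assuming complete mediation and should not be read as the expected result. The harm is confined to the PN coefficient in this regression. The wording should be corrected before the analysis, because the missing threshold and retention rule otherwise leave the choice to be made after the data are seen.

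**What to change.** In the Statistical Analysis Plan, Aim 2:

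1. Define a mediator as a post-randomization variable that is affected by arm and in turn affects the outcome.
2. For randomized patients, replace the change-in-estimate step with an arm-effect model holding arm and a few prespecified pre-randomization covariates, within the limit of 4 predictors. Arm, baseline biomarker, center and baseline severity make 4 if center is one indicator term. Not every reasonable covariate fits: age group and BMI z-score group, each with three levels, would alone take 2 + 2 = 4 terms, or 5 with arm.
3. Keep post-randomization variables, including EN/PN dose and route, out of that model. Report any mediation analysis separately and label it exploratory.
4. Keep the interaction terms for effect modification. Each one uses a predictor, so state which covariate gives way.
5. Restrict any confounding assessment to the non-randomized usual-care patients who would enter Aim 2 if Aim 1 is stopped.

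The cost is a change of SAP wording, with no new data or patients. The downside is that fewer covariates can be explored in the arm model.
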